## Design

This feasibility study was a community-based participatory research design with two phases, namely, a development phase and an implementation phase. The development phase included a 4-month preparation phase, where study staff worked with a community engagement group to modify a working Virtual Reality (VR) randomized controlled trial home-based protocol to a local public high school setting. The 9-month implementation phase utilized a “learn-as-you-go” approach with a single group pre- to post-trial design to test the implementation of the developed VR HMD (Head Mount Display) school-based protocol. The study was implemented at a public high school within the United States, which had adapted education support for children with special needs. The study was approved by the University Institutional Review Board prior to enrolling participants. Participants had to provide informed consent and assent documentation prior to joining the study. The principal of the high school approved and supported the study.

## Participants

This feasibility study aimed to recruit a convenient sample of 12 participants, which is a general recommendation for exploratory studies targeting implementation process metrics, as opposed to group-effect comparisons that would need larger samples. Eligibility criteria are listed below. Participants were recruited through word-of-mouth and flyers by the community engagement group (case manager and young adult).

Inclusion criteria for the study included:

1. Between the ages of 10-19 years of age
2. Enrolled in school special education or self-reported disability
3. Note from physician permitting participation in moderate-intensity exercise or cleared for sports participation through physical examination that was on file by the school
4. Ability to communicate in English (or a caregiver)

Exclusion criteria for the study included:

1. Complete blindness or deafness

## 2. Condition that may make participation unsafe

### Supplies

Participants used a VR HMD for exercise (Quest 3, Meta, USA), which came with two hand-held controllers. Active video games were purchased through the Meta Oculus digital cloud server. The games were purchased for a standard Meta account created for the study. Games included Beat Saber, Les Mills Body Combat, Creed: Rise to Glory, Smash Drums, Power Beats VR, and Thrill of the Fight.

### Intervention Development and Protocol

During the development phase of the study, the community engagement group worked with the research team to modify a home-based VR HMD clinical trial protocol [20] to be more easily implemented in a high school setting. In summary, the original intervention prescription included 150 minutes of moderate-intensity activity per week using the Quest 3 at home, for a total of 12 weeks. Home exercise was supported by theory-driven behavioral tele coaching calls. In that study, caregivers were the primary intervention agents who managed their child's exercise schedules and study activities.

Through the four-month development phase for the present study, meetings with the community engagement group resulted in the following finalized exercise protocol to test in high school:

- Frequency: three times per week
- Intensity: moderate intensity exercise as indicated by a rating of perceived exertion of 5 to 7 on the Borg 0-10 scale
- Time: as many minutes of exercise as possible that could be fit within students' school schedules (e.g., either within their physical education period or a study hall or gap period)
- Type: VR exercise at home or in the school setting, at the choice of the caregiver and participant. At enrollment, caregivers were asked whether they preferred the child to perform the exercise at school or home with a borrowed headset. Home-based participants were not given more attention than those who exercised at school. For example, no behavioral coaching calls were given to home participants as is done in the protocol from which the present study was modified.

### Intervention Procedures

Participants and their caregivers who were interested in the program were referred to study staff by the community engagement case manager. Participants were contacted by research staff and screened through phone calls. Eligible participants were directed to an online electronic data capture platform (REDCap) to provide informed consent and assent, participant demographics, and complete the physical activity survey. Next, they were scheduled for an onsite visit at the school to complete the physical fitness tests. Next, study staff scheduled the exercise sessions within a gap period or physical education period for participants who chose to exercise at school. Exercise sessions were performed

at the school for six weeks, and all sessions were supervised by at least one research team member. For participants who chose to exercise at home, they were provided with a Quest 3 with the preinstalled games in a convenient carrying case. They were provided with the same exercise prescription as those who chose to exercise in the school. Home-based participants were not provided with additional attention or behavioral coaching. Quest 3 headsets were returned to the school once the home-based participant completed the six-week program.

## Measures

### Participant Characteristics

Age, sex, height, weight, and ethnicity were descriptively reported for the enrolled participants. The use of a mobility device and wheelchair was recorded. As a gauge for how physically active participants were upon joining the study, physical activity level was measured using the NIH PROMIS Pediatric Physical Activity Short Form 8-item survey. The survey results in a total T-score. T-scores range from 20-80, with a mean of  $50 \pm 10$ . A higher T-score indicates high levels of participation in physical activity. Scores that were  $0.5-1$  SD below the mean indicate “mild” difference or impairment; scores  $1.0-2.0$  SD below the mean, “moderate” impairment; scores  $\geq 2.0$  SD below the mean, “severe” impairment.

## Research Question 2: Student Attendance

Student attendance was expressed as a percentage value, measured by the number of exercise sessions attended, divided by the total sessions prescribed. The exercise prescription was a total of 18 sessions, broken up into three sessions per week for six weeks.

## Research Question 3 and 4: Student Enrollment and Payment Incentives

Student enrollment was measured by the number of students enrolled per school semester. The program lasted a total of two school semesters and was completed prior to summer break. Payment incentives were planned to be increased if the target sample size of 12 was not met from the first school semester. Payment incentives started at \$50 for each of the two data collection visits, for a total of \$100. Because of inadequate enrollment in the first semester, the payment incentive for the second semester was increased to \$100 per data collection visit, for a total of \$200.

## Research Question 5: Potential Effect Estimates of the Program on Physical Fitness Tests

Physical fitness was measured by walking endurance and hand-grip strength. Walking endurance was measured using a six-minute walk test (6MWT). A six-minute push test was planned to be used for students who used wheelchairs, but this was never utilized. The 6MWT measures the distance walked within six minutes around a designated course. The course was a long unobstructed hallway that allowed the participant to freely walk for the duration of the test. When participants reached the end of the hall they were instructed to turn and continue down the hallway. The rationale for choosing this location was that the study staff found there was limited space to set up and conduct a larger circular track during school hours, particularly without interference from other students. The 6MWT is suggested to be valid and reliable among children without disabilities. However, the 6MWT has conflicting evidence regarding validity for various pediatric clinical groups. Hand-grip strength was measured by the mean value of three maximal grip trials on a hand-held dynamometer (Camry Digital Hand Dynamometer, Camry, USA), while the participant was in a seated position. Grip-strength has evidence to support its use among children with intellectual disabilities.

## Research Question 6: Ideal Exercise Environment

To identify the ideal method for how schools can implement the exercise program for students in a future trial, outcomes were compared between exercise settings (home versus school). Compared outcomes included enrollment, exercise volume, attendance, and fitness tests.

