## Analyses

Descriptive statistics, including means, standard deviations, and confidence intervals, were obtained for all study variables. Changes in means were compared primarily using descriptive comparisons with 95% confidence intervals, with t-tests as appropriate. Analyses were performed using IBM SPSS Statistics version 29. Qualitative data were analyzed using a thematic analysis approach.

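### Research Question 6 is meant to pick an ideal setting from home-versus-school outcomes, but families chose the setting and the target of 12 was not justified for group comparisons

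*Combined protocol and SAP*

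**What the plan says.** - **Purpose.** Research Question 6: "To identify the ideal method for how schools can implement the exercise program for students in a future trial, outcomes were compared" between home and school. The outcomes listed are enrollment, exercise volume, attendance and the fitness tests.
- **Design.** The Design section describes a "single group pre- to post-trial design to test the implementation of the developed VR HMD" school-based protocol. It sets up no controlled comparison of settings.
- **Sample size.** The Participants section says "This feasibility study aimed to recruit a convenient sample of 12 participants", and justifies that number for studies "targeting implementation process metrics, as opposed to group-effect comparisons that would need larger samples".
- **How setting was decided.** Intervention Development and Protocol gives the type of exercise as "VR exercise at home or in the school setting, at the choice of the caregiver and participant". The preference was asked at enrollment.
- **Delivery.** Intervention Procedures says of the school program that "all sessions were supervised by at least one research team member". Home participants took a headset home and received the same prescription, with no extra attention or coaching. No supervision at home is described.
- **Baseline data.** Participant Characteristics says "Age, sex, height, weight, and ethnicity were descriptively reported for the enrolled participants". It does not say whether they are shown by setting.
- **Analysis.** The Analyses section says "Changes in means were compared primarily using descriptive comparisons with 95% confidence intervals", with t-tests where suitable. It attaches no test to the home-school contrast and mentions no adjustment.

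**The concern.** The stated purpose is comparative and has a named use: deciding how schools should deliver the program in a future trial. The groups being compared formed themselves. Families who preferred home may differ from those who preferred school in ways related to how much the student exercises, how many sessions are completed, or how fitness changes. A difference between settings could come from the setting, from the families who chose it, or from research staff being present at school. This design cannot separate the three. The contrast would also be very imprecise. The risk is that a future trial fixes its delivery setting on a difference that reflects which families chose which setting.

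**Working it through.** **Step 1: purpose against design.** The plan gives no figure for the home-school contrast, so there is none to reproduce. The argument rests on how its sections fit together.

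- *Allocation.* Family choice means that baseline differences between settings are possible. The text available for review includes no adjustment, no stated baseline table by setting and no limit on interpretation. It equalizes only attention, coaching and prescription.
- *Sample size.* The Participants section sets group-effect comparisons aside. The conflict is clearest for the fitness tests, where comparing settings is a group-effect comparison. Attendance and volume can be read as process metrics. They are useful for describing families who choose each setting, but not for ranking the settings.
- *Delivery.* The contrast is between two packages: school with research-staff supervision, and home with none described. Supervision by research staff does not show how a school would run the program with its own staff.
- *Enrollment.* The proportion choosing each setting is itself the preference measure, so self-selection does not bias it.

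**Step 2: precision of a between-setting mean difference (illustration).** The target of 12 is from the Participants section. The split, the number analyzed and equal SDs are assumptions. Results are in SD units of the outcome (for fitness, of the change).

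Half-width = t(0.975, n1+n2−2) × √(1/n1 + 1/n2). With 12 analyzed, t(0.975, 10) = 2.228.

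- 6:6: 2.228 × √(1/6 + 1/6) = 2.228 × 0.577 = 1.29 SD
- 8:4: 2.228 × √(1/8 + 1/4) = 2.228 × 0.612 = 1.36 SD
- 9:3: 2.228 × √(1/9 + 1/3) = 2.228 × 0.667 = 1.49 SD
- 10:2: 2.228 × √(1/10 + 1/2) = 2.228 × 0.775 = 1.73 SD

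Even at the most favorable split, an observed difference of zero would have an interval from −1.29 to +1.29 SD. If only 8 are analyzed, the half-width is 1.73 SD at 4:4 and 2.00 SD at 6:2.

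If equal SDs are not assumed (Welch, taking the two sample SDs as equal), the half-width is 1.29 SD at 6:6 and 1.97 SD at 9:3 (3.46 degrees of freedom). At 10:2 it is 4.97 SD on 1.43 degrees of freedom, mainly because two participants say little about their own SD.

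**Step 3: precision of the preference estimate.** Exact (Clopper-Pearson) 95% intervals for assumed counts: 6/12 = 50% (21% to 79%); 10/12 = 83% (52% to 98%). These are wide too, but the quantity is one that the design can estimate.

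**Step 4: would more participants solve it?** Only the precision. A larger self-selected sample would still mix the effect of setting with the effect of family choice.

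**The case against.** The strongest defense has four parts.

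1. *This is a feasibility study with a descriptive analysis.* This stands in part. The Analyses section relies mainly on description with confidence intervals, so imprecision would be visible. Research Question 6 sets no threshold or decision rule. But a descriptive method does not support an ideal-method conclusion when the groups chose themselves.
2. *Choice of setting is part of the program.* This also stands in part. If a future program offers the same choice, attendance and volume among those choosing each setting help planning. They still do not show that one setting is better than the other.
3. *Silence is not proof of omission.* This stands as a limit. Parts of the document were removed before review and no limitations section is present, so the absence of a caveat can be claimed only for the supplied text. Likewise, baseline data by setting may be reported even though the plan does not say so.
4. *The precision figures are hypothetical.* They are: the split is assumed, and no outcome SD is given, so nothing can be put in meters, kilograms or minutes. They illustrate a limit that the Participants section already acknowledges.

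A reader might also infer that the plan commits to an underpowered significance test between settings. The documents do not support that: t-tests are mentioned only in general terms and none is tied to this contrast.

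**Conclusion.** The concern holds as a mismatch between what Research Question 6 is meant to conclude and what the design can support. Volume, attendance and fitness differences between self-selected settings, one of them supervised by research staff, are not evidence that either setting is better. The mismatch with the sample-size rationale is firm for the fitness tests and arguable for attendance and volume.

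On size: with 12 analyzed and equal SDs, a between-setting difference would carry a 95% half-width of 1.29 to 1.73 SD over assumed splits from 6:6 to 10:2. Fewer participants would widen it.

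It would go too far to infer that following the plan must produce a false claim, or that the study is invalid. No stated figure is wrong, the analysis is already mainly descriptive, and the setting comparison is one of seven research questions. The point is worth correcting because the intended use is a design decision for a later trial.

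**What to change.** 1. Restate Research Question 6 as: describe setting preference and delivery by chosen setting.
2. Report the proportion of enrolled participants choosing each setting, with an exact 95% CI.
3. For each setting, report group size, baseline characteristics, and summaries of exercise volume, attendance and fitness change. Show any between-setting difference with its 95% CI, labeled descriptive and hypothesis-generating, and say whether equal SDs were assumed. A group needs at least two participants to have its own SD.
4. State that differences are confounded by family choice and by research-staff supervision at school.
5. Draw no ideal or superiority conclusion from these outcome differences.
6. Because the document is written in the past tense, disclose this as a change made after the plan was written.

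**Cost.** Analysis and report wording only, using data already collected. The report can no longer name an ideal setting from these outcomes, and the intervals it shows will probably be wide.

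### RQ6 compares school sessions that research staff scheduled and supervised with home sessions where none is described, so it cannot separate place from staffing or show delivery by school personnel

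*Combined protocol and SAP*

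**What the plan says.** Research Question 6, headed Ideal Exercise Environment, gives the aim and the method together: "To identify the ideal method for how schools can implement the exercise program for students in a future trial, outcomes were compared between exercise settings". It then lists what is compared: "Compared outcomes included enrollment, exercise volume, attendance, and fitness tests".

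Intervention Procedures describes how each setting was run. For school, "study staff scheduled the exercise sessions within a gap period or physical education period for participants who chose to exercise at school", and sessions took place "at the school for six weeks, and all sessions were supervised by at least one research team member". For home, the description is of equipment: "For participants who chose to exercise at home, they were provided with a Quest 3 with the preinstalled games in a convenient carrying case". Home participants had the same prescription, and "Home-based participants were not provided with additional attention or behavioral coaching".

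Intervention Development and Protocol adds that setting was chosen by the family ("VR exercise at home or in the school setting, at the choice of the caregiver and participant") and gives one statement about balance of attention: "Home-based participants were not given more attention than those who exercised at school". The Analyses section plans descriptive comparisons with 95% confidence intervals, with t-tests where appropriate. It says nothing about staffing.

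**The concern.** RQ6 treats its contrast as one of place, and its heading invites the reader to credit any difference to the environment. The delivery text shows that the two conditions also differed in whether research staff arranged and attended the sessions. Attendance and exercise volume are plausibly sensitive to having someone book a slot and be present for it, and fitness change could follow from both.

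Two conclusions are at stake. If the school figures look better, a future trial might choose school because of its setting when the staffing produced the result, or set home aside after it was tried without comparable support. And because RQ6 asks how schools can implement the program, its results may be taken as evidence about delivery by a school's own personnel, which the documents do not describe happening.

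**Working it through.** The plan gives no figure to reproduce here. The check is whether the design as described can support the contrast that RQ6 names.

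**Inputs**
- Prescribed sessions: 18 (Research Question 2).
- Maximum active minutes at school: 75 per week (Research Question 1).
- School sessions supervised by research staff: all of them (Intervention Procedures).
- Home sessions with research staff present: none described (Intervention Procedures; Intervention Development and Protocol).
- Documented school-linked roles: approval and support by the principal (Design); recruitment and referral through the community engagement case manager (Participants; Intervention Procedures). Neither is session delivery.

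**Step 1: exposure to research staff at full attendance**
- Sessions: 3 per week × 6 weeks = 18, which agrees with the stated prescription.
- School: 18 of 18 staffed, covering up to 75 × 6 = 450 active minutes.
- Home: 0 of 18 described as staffed.

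**Step 2: which combinations of place and staffing were observed**

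| | Research staff present | No research staff |
|---|---|---|
| School | observed | none |
| Home | none described | observed |

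Only one diagonal of the table is filled. The empty school cell is the one that would have to hold sessions run by school personnel alone.

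**Step 3: what the contrast estimates**

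Write a participant's expected outcome as a + b × (school) + c × (research staff), where each indicator is 0 or 1. Here the two indicators are equal for every participant, so

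- school mean = a + b + c
- home mean = a
- difference = b + c.

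Only the sum can be estimated. The two columns of the design matrix are identical at the target of 12 participants or at any larger number, so neither adjustment nor more data splits b from c. The same would hold if setting had been assigned at random. Choice of setting by families is a separate source of confounding, and this argument does not depend on it.

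**Step 4: which outcomes are touched**
- Attendance, exercise volume and fitness change all arise during or after the staffed sessions, so they are fully affected.
- Enrollment by setting reflects a preference stated at enrollment, before any session, so it is less affected.

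**Step 5: whether anything elsewhere repairs it**
- The attention statement runs one way. It rules out more attention at home, while the imbalance in Step 1 is toward school.
- The analysis plan contains no term or stratum for staffing, and by Step 3 none would help.
- Research Question 7 interviews the interventionists about barriers and facilitators at school. That gives useful context but does not observe school-run sessions.

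**The case against.** The strongest defence is that this is a small, single-group, learn-as-you-go feasibility study. It sized itself for process measures and disclaims group-effect comparisons, its analysis is mainly descriptive, and it discloses the staffing openly. RQ6 also looks ahead to a future trial, which may again be run by research staff. For that purpose, comparing two whole delivery packages is a reasonable thing to do. That part stands: the comparison has a legitimate use, and the defect lies in how the contrast is named and what is concluded from it.

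A reader might also infer more than the documents support:

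- *That the study sets up adoption by schools on these results.* The aim is tied to a future trial, and no section proposes adoption.
- *That lack of coaching calls is a difference between the settings.* The calls belonged to the source home protocol. They were dropped for home participants, and no section gives them to school participants either.
- *That home sessions were unsupervised.* The text supports only that no research staff are described. It does not say whether caregivers were present.
- *That all of RQ6 is equally compromised.* Enrollment by setting precedes any session.
- *That a school advantage would be due to staffing.* The design cannot show this any more than it can show an effect of place.

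None of these limits removes the central point. Open disclosure in the procedures does not change the label or the aim in RQ6, and descriptive reporting of an aliased contrast is still aliased.

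**Conclusion.** The concern holds for attendance, exercise volume and fitness change. For these outcomes setting is completely aliased with research staffing (18 of 18 prescribed sessions against none described), so RQ6 as written cannot identify an ideal environment. No session run by school personnel alone is described, so the data do not show that form of delivery. The comparison remains informative about two delivery packages, and hence for a future trial staffed in the same way.

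The 18-to-0 figure measures the difference in planned exposure. It is not an estimate of bias, and the documents allow none. The conclusion rests on one explicit statement, that all school sessions were supervised by the research team, and on one inference, that no research staff attended home sessions. The inference is strong, since home delivery is described only as equipment and a prescription without added attention, but no sentence states it outright. The point merits a change because the correction alters what RQ6 may conclude and costs almost nothing.

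**What to change.** In Research Question 6:

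1. Name the conditions by what was delivered: *research-staff-scheduled and supervised sessions at school* and *home sessions without research staff*.
2. Restate the aim as describing outcomes under these two delivery packages, to inform a future trial.
3. State that no conclusion is drawn about place apart from research staffing, or about delivery by school staff.
4. Report the number of research staff present per school session if study records allow. The documents give only a minimum of one and describe no staffing log, so this item is conditional.

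Items 1 to 3 are wording only and need no new data or reanalysis. The downside is that RQ6 can no longer claim to identify an ideal environment.
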